### **8.5.7 Safety Monitoring for Documented Hyperglycemia**

Subjects will be asked to self-monitor their glucose at least once a week and reviewed by Investigator at each Study Center visit. If the value exceeds the specific glycemic limit specified below, the subject will be instructed to check again during the 2 following days. If all values in 3 consecutive days exceed the specific limit, the subject should contact the Investigator and a central laboratory FPG measurement will be performed).

The threshold values are defined as follows, depending on study period:

From Baseline visit to Week 13 (including value at Week 13) of Randomized Treatment period:

- Blood Glucose  $> 270$  mg/dL (15.0 mmol/L)

From Week 13 to Post-treatment Follow-up (Week 4, 8 and 13 post end of treatment period):

- Blood Glucose  $> 240$  mg/dL (13.3 mmol/L) or
- HbA1c  $> 9\%$  (for subjects with Baseline HbA1c  $< 8\%$ ) and HbA1c increase of more than 1% from Baseline (for subjects with Baseline HbA1c  $\geq 8\%$ )

In case of blood glucose/HbA1c above the threshold values, the Investigator should ensure that no reasonable explanation exists for insufficient glucose control and in particular that:

- Blood glucose was actually measured in the fasting condition
- Absence of intercurrent disease which may jeopardize glycemic control. In case of an emergency such as unplanned hospitalization (e.g., surgery, infection), the Investigator

can take appropriate measures for glycemic control. If the measure does not exceed 7 days, then it will not be considered a rescue. If the measure lasts beyond 7 days then it will be treated as a rescue

- Compliance to treatment is appropriate
- Compliance to diet and lifestyle is appropriate

If any of the above can reasonably explain the insufficient glycemic control, the Investigator should undertake appropriate action, i.e.:

- Investigation and treatment of intercurrent disease (to be reported in AE/concomitant medication parts of the eCRF)
- Stress on the absolute need to be compliant to treatment
- Organize a specific interview with a Registered Dietician or other qualified nutrition professional and stress on the absolute need to be compliant to diet and lifestyle recommendations
- Schedule an FPG/HbA1c assessment at the next visit

If none from the above-mentioned reason can be found, or if appropriate action fails to decrease blood glucose/HbA1c under the threshold values, rescue medication may be introduced at the Investigator discretion and according to local guidelines.

All assessments for primary and secondary efficacy and safety parameters planned in final primary endpoint assessment visit should be performed before adding the rescue medication if possible. Then the subject continues the study treatment and stays in the study in order to collect safety information. The planned visits and assessments should occur until the last scheduled visit. (See more details in [Appendix A](#)).

Note: After Study Drug discontinuation any treatments are permitted, as deemed necessary by the Investigator.

## 8.6 Stopping Rules

For the purposes of stopping rules, Baseline is defined as the average of Day 1 pre-dose assessment and the last measurement prior to Day 1.

### 8.6.1 Stopping Rules for Liver Chemistry Elevations

In the event of confirmed laboratory results meeting any of the following criteria, dosing of a subject with Study Drug will be stopped permanently:

1. ALT or AST > 8 x ULN, which is confirmed
2. ALT or AST > 5 x ULN, which is confirmed and persists for  $\geq 2$  weeks
3. ALT or AST > 3 x ULN (or the greater of 2 x Baseline value or 3 x ULN if the Baseline value was > ULN), which is confirmed **and** total bilirubin > 2 x ULN or INR > 1.5
4. ALT or AST > 3 x ULN (or the greater of 2 x Baseline value or 3 x ULN if the Baseline value was > ULN), which is confirmed, and the new appearance (i.e., onset coincides with the changes in hepatic enzymes) of fatigue, nausea, vomiting, right upper quadrant

pain or tenderness, fever, rash, or eosinophilia ( $> \text{ULN}$ ) felt by the Investigator to be potentially related to hepatic inflammation/injury

### **8.6.2 Stopping Rules for Renal Function Test Results**

In the event of an eGFR (by CKD-EPI formula) meeting any of the following criteria, or any change in renal biomarkers deemed by the investigator to require further evaluation, a serum creatinine, urine culture, and urine microscopy sample with inspection of sediment should be immediately obtained.

Dosing of a subject with Study Drug (ISIS 703802 or placebo) will be stopped permanently if testing in any of the following values is confirmed in the absence of an alternative explanation:

1. eGFR (CKD-EPI) decrease of  $> 25\%$  from Baseline
2. eGFR (CKD-EPI) value  $< 45 \text{ mL/min/1.73 m}^2$
3. UACR  $> 165 \text{ mg/g}$
4. UPCR  $> 325 \text{ mg/g}$
5. New onset of hematuria (defined as  $\geq 5 \text{ RBC/hpf}$ )

Irrespective of whether the stopping rule is confirmed or not, the follow-up schedule and frequency of renal function monitoring after the initial event will be determined by the Study Medical Monitor in consultation with the Investigator. The Investigator should consider consulting a local nephrologist for any change of renal function that presents a concern. If a renal biopsy is performed, a sample specimen should be made available for examination by an independent renal pathologist who has been engaged by the Sponsor to review such specimens.

### **8.6.3 Stopping Rule for Platelet Count Results**

Actions to be taken in the event of a low platelet count are summarized in [Table 3](#) below.

In the event of any platelet count  $< 50,000/\text{mm}^3$ , or a platelet count less than  $75,000/\text{mm}^3$  that occurs while the subject is already on reduced dose, dosing of the subject with Study Drug will be stopped permanently ([Table 3](#)). Platelet count will be monitored daily until 2 successive values show improvement then monitored every 2-3 days until platelet count is stable.

Administration of steroids is recommended for subjects whose platelet count is less than  $25,000/\text{mm}^3$ . Recovery in platelet count may be accelerated by administration of high dose steroids. Treatment guidelines for immune thrombocytopenia ([Provan et al. 2010](#)) recommend Dexamethasone 40 mg daily for 4 days every 2-4 weeks for 1-4 cycles; Prednis(ol)one 0.5-2 mg/kg/d for 2-4 weeks then taper; or methylprednisolone 30 mg/kg/day for 7 days (**note:** may require continuation with oral steroids after methylprednisolone).

In the event of a platelet count  $< 75,000/\text{mm}^3$  and  $\geq 50,000/\text{mm}^3$ , dosing of a subject with Study Drug should be suspended temporarily until the platelet count has recovered to  $\geq 100,000/\text{mm}^3$ . If dosing is continued, it must be at a reduced dose as shown in [Table 3](#). The suitability of the subject for continued dosing will be determined by the Investigator in consultation with the Study Medical Monitor and will be based on factors such as the original rate of decline in the subject's platelet count, whether any bleeding events were experienced by the subject, and the speed of recovery of platelet count after interruption of dosing.

If, after reintroduction of Study Drug, the platelet count again falls below  $75,000/\text{mm}^3$ , then dosing of the subject with Study Drug will be stopped permanently.

Once a subject commences weekly monitoring, this frequency of monitoring should continue until the platelet count returns to the normal range ( $\geq 140,000/\text{mm}^3$ ) for 2 successive values.

Any unreportable platelet count result must be rechecked and determined not to have met a stopping rule before dosing can continue.

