**Table 3 Actions in Subjects with Low Platelet Count**

Platelet Count on Rx	Drug Dose	Monitoring
Normal range, $\geq 140\text{K}/\text{mm}^3$	No action	Monitor every 14 days (+/- 2 days)
$\geq 100\text{K}$ to $<140\text{K}/\text{mm}^3$	No action	Closer observation Monitor every week*
$\geq 75\text{K}$ to $<100\text{K}/\text{mm}^3$	Permanently reduce the dose by 50 % as follows: For Cohort A: reduce to 10 mg every week For Cohort B: reduce to 20 mg every 4 weeks For Cohort C: reduce to 40 mg every 4 weeks	Closer observation Monitor every week*
$\geq 50\text{K}$ to $<75\text{K}/\text{mm}^3$	Pause dosing When platelet count returns to $> 100\text{K}/\text{mm}^3$ restart dosing as follows only if approved by Sponsor Medical Monitor: For Cohort A: reduce to 10 mg every week For Cohort B: reduce to 20 mg every 4 weeks For Cohort C: reduce to 40 mg every 4 weeks  or Permanently discontinue Study Drug if it occurs while on already reduced dose	Closer observation Monitor every 2-3 days until 2 successive values show improvement Consider discontinuation of antiplatelet agents/non-steroidal anti-inflammatory drug (NSAIDS)/ anticoagulant medication
$\geq 25\text{K}$ to $<50\text{K}/\text{mm}^3$	Permanently discontinue Study Drug	Closer observation: Monitor daily until 2 successive values show improvement then monitor every 2-3 days until platelet count stable Discontinue antiplatelet agents/NSAIDS/anticoagulant medication while platelet count $< 50\text{K}/\text{mm}^3$ if possible Refer to hematologist to provide diagnostic and therapeutic management
$< 25\text{K}/\text{mm}^3$	Permanently discontinue Study Drug	Closer observation: Monitor daily until 2 successive values show improvement then monitor every 2-3 days until platelet count stable Steroids recommended** Consider need for hospitalization Discontinue antiplatelet agents/NSAIDS/anticoagulant medication while platelet count $< 50\text{K}/\text{mm}^3$ if possible Refer to hematologist to provide diagnostic and therapeutic management

\* Once a subject commences weekly monitoring this frequency of monitoring should continue until the platelet count returns to the normal range ( $\geq 140,000/\text{mm}^3$ ) for 2 successive values.

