### **8.8.1 *Follow-up Visits for Early Termination from Treatment Period or from Post-Treatment Follow-up Period***

Any subject who discontinues early from the treatment period or from post-treatment follow-up period should be followed as per the platelet monitoring rules shown in, [Section 8.6.3](#) for the first 6 weeks after discontinuing Study Drug and then at 8 (weekly dosing cohort) or 10 (every 4 week dosing cohorts) and 13 weeks post end of treatment period (as per visit schedule).

If the subject declines or is unable to participate in the above, the early termination visit procedures should be performed at the time of withdrawal, at a minimum, and ideally within 2 weeks from the last dose of Study Drug.

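### For a platelet count of 50,000 to below 75,000/mm³ on a reduced dose, protocol Section 8.6.3 and its Table 3 set different monitoring schedules after the permanent stop

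*Protocol*

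**What the plan says.** Protocol Section 8.6.3 opens by presenting Table 3 as its summary: "Actions to be taken in the event of a low platelet count are summarized in" that table. One sentence of the text then names two triggers for a permanent stop. The first is any count below 50,000/mm³. The second is a count below 75,000/mm³ "that occurs while the subject is already on reduced dose, dosing of the subject with Study Drug will be stopped permanently". The next sentence, in the same paragraph, sets the follow-up: "Platelet count will be monitored daily until 2 successive values show improvement then monitored every 2-3 days until platelet count is stable".

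Table 3 places the second trigger in its row for 50,000 to below 75,000/mm³. The dose cell offers a pause with a possible restart, or the alternative: "Permanently discontinue Study Drug if it occurs while on already reduced dose". One monitoring cell serves both branches: "Closer observation Monitor every 2-3 days until 2 successive values show improvement". The daily schedule, "Monitor daily until 2 successive values show improvement then monitor every 2-3 days until platelet count stable", appears only in the two rows below 50,000/mm³.

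**The concern.** The text and the table describe the same event and agree on the dosing action, but they differ on how often platelets are counted afterwards and on when that phase of counting ends. The table is offered as a summary, so a reader would expect it to match.

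The rule matters because protocol Section 2.5.2 relies on the platelet monitoring and stopping rules to mitigate a known risk of the drug class, including severe thrombocytopenia with unconjugated compounds. The synopsis also lists the incidence of platelet reductions among the safety considerations for dose selection. With two required schedules for one event, a study monitor could not say which site had deviated. The efficacy analyses do not depend on it.

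**Working it through.** There is no stated figure to reproduce. The check compares the two sources, looks for a rule that settles the difference, and counts samples under each schedule.

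**Same event, two schedules** (50,000 to below 75,000/mm³, already on a reduced dose)

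| | Section 8.6.3 text | Table 3 row |
|---|---|---|
| Dosing | Permanent stop | Permanent stop |
| First phase | Daily until 2 successive values improve | Every 2-3 days until 2 successive values improve |
| Second phase | Every 2-3 days until stable | None stated in the row |

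The conflict is confined to subjects already on a reduced dose. For a fall into this band on full dose, the text gives only a temporary suspension and does not attach the daily schedule.

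**Is there a tie-breaker?**

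- Section 8.5.3 sends the reader to Table 3 for actions.
- Section 8.8.1 says that subjects who discontinue early "should be followed as per the platelet monitoring rules shown in" Section 8.6.3 for the first 6 weeks. That section contains both schedules.
- A later paragraph of Section 8.6.3 repeats the permanent stop for a renewed fall below 75,000/mm³ after reintroduction, with no schedule attached.
- Sections 3.4, 6.2 and 8.5 provide Medical Monitor involvement but do not rank text against table.
- SAP Section 2.4.1 refers back to protocol Sections 8.5 to 8.7 and adds no rule.

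**Counts in the first week.** Assumptions: triggering count on day 0; days 1 to 7 counted; visits exactly on schedule; count not yet judged stable within the week; only the schedules above counted, not confirmatory retests or rules for other rows.

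*Immediate improvement (each new value better than the last):*

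- Text: days 1 and 2 end the daily phase. Then every 2 days gives days 4 and 6, so 2 + 2 = 4 counts; every 3 days gives day 5, so 2 + 1 = 3 counts.
- Table: days 2 and 4, or days 3 and 6, so 2 counts.
- Ratio: 4/2 = 2 at 2-day spacing; 3/2 = 1.5 at 3-day spacing.

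*No improvement during the week:*

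- Text: days 1 to 7, so 7 counts.
- Table: days 2, 4 and 6 (3 counts), or days 3 and 6 (2 counts).
- Ratio: 7/3 = 2.3, or 7/2 = 3.5.

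The earliest day on which two successive improving values can be seen is day 2 under the text, and day 4 (2-day spacing) or day 6 (3-day spacing) under the table.

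**The case against.** The strongest reply is that the daily sentence was meant only for counts below 50,000/mm³, which is where Table 3 puts it. That is possible, but the text does not say so: the sentence follows both triggers without restriction. If that was the intent, the text needs the edit; if not, the table does.

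The second reply is that sites do not act alone, and this largely stands. Every affected count is below the 140,000/mm³ alert level in Section 8.5.3. Under Section 6.2, the Sponsor and CRO Medical Monitors agree on actions and send instructions within 24 hours of an actionable alert. Section 8.5 asks for a repeat specimen, ideally within 3 days, and a full evaluation in consultation with the Study Medical Monitor. Section 3.4 lets the Study Medical Monitor set the frequency of additional monitoring. These provisions limit the harm, but they do not remove the mismatch.

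The third reply is that counting does not simply cease when the row's schedule ends. The rows from 75,000 to below 140,000/mm³ call for weekly counts, and weekly monitoring, once begun, continues until two successive values are at least 140,000/mm³. Section 8.8.1 also sets later visits. This stands: the gap is the missing daily phase and an earlier end to the 2-3-day phase.

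**Conclusion.** The inconsistency is real and small. Read as written, the protocol sets two required schedules for one event, and nothing in the documents ranks them. In the first week the difference is about 3 to 4 counts against 2 with immediate improvement, and 7 against 2 to 3 with none, under the assumptions stated above. The number of subjects affected is expected to be small, though the documents give no figure for it.

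A reader might infer more, and four such readings are not supported:

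- **Sites will in practice follow the table.** No passage says so. Section 8.5.3 points to the table, but Medical Monitor instructions may decide the schedule.
- **The table gives 2 to 3 times fewer counts until recovery.** The text's daily phase ends at two successive improving values, not at recovery, and the ratio varies with the course of the count.
- **The event is always a second platelet fall.** Section 8.7 also allows dose reduction for other safety or tolerability reasons.
- **The restart threshold is part of this conflict.** A permanent stop has no restart. The difference (at or above 100,000/mm³ in the text, above 100,000/mm³ in the table) belongs to the pause branch. It matters only at exactly 100,000/mm³.

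**What to change.** The clinical team should reconcile the Section 8.6.3 text with the Table 3 row for 50,000 to below 75,000/mm³, so that a subject already on a reduced dose has one monitoring frequency and one end point after the permanent stop. If the pause and permanent-stop branches are meant to have different schedules, the row's single monitoring cell should be split. If the daily sentence is meant for only one trigger, the text should name it. As a separate minor edit, align the restart wording for the pause branch. Which schedule and which threshold are right is for the clinical team to decide.

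The cost is protocol wording in two places. The sample size, the randomization and the efficacy analyses are unchanged.

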**Table 3 Actions in Subjects with Low Platelet Count**

Platelet Count on Rx	Drug Dose	Monitoring
Normal range, $\geq 140\text{K}/\text{mm}^3$	No action	Monitor every 14 days (+/- 2 days)
$\geq 100\text{K}$ to $<140\text{K}/\text{mm}^3$	No action	Closer observation Monitor every week*
$\geq 75\text{K}$ to $<100\text{K}/\text{mm}^3$	Permanently reduce the dose by 50 % as follows: For Cohort A: reduce to 10 mg every week For Cohort B: reduce to 20 mg every 4 weeks For Cohort C: reduce to 40 mg every 4 weeks	Closer observation Monitor every week*
$\geq 50\text{K}$ to $<75\text{K}/\text{mm}^3$	Pause dosing When platelet count returns to $> 100\text{K}/\text{mm}^3$ restart dosing as follows only if approved by Sponsor Medical Monitor: For Cohort A: reduce to 10 mg every week For Cohort B: reduce to 20 mg every 4 weeks For Cohort C: reduce to 40 mg every 4 weeks  or Permanently discontinue Study Drug if it occurs while on already reduced dose	Closer observation Monitor every 2-3 days until 2 successive values show improvement Consider discontinuation of antiplatelet agents/non-steroidal anti-inflammatory drug (NSAIDS)/ anticoagulant medication
$\geq 25\text{K}$ to $<50\text{K}/\text{mm}^3$	Permanently discontinue Study Drug	Closer observation: Monitor daily until 2 successive values show improvement then monitor every 2-3 days until platelet count stable Discontinue antiplatelet agents/NSAIDS/anticoagulant medication while platelet count $< 50\text{K}/\text{mm}^3$ if possible Refer to hematologist to provide diagnostic and therapeutic management
$< 25\text{K}/\text{mm}^3$	Permanently discontinue Study Drug	Closer observation: Monitor daily until 2 successive values show improvement then monitor every 2-3 days until platelet count stable Steroids recommended** Consider need for hospitalization Discontinue antiplatelet agents/NSAIDS/anticoagulant medication while platelet count $< 50\text{K}/\text{mm}^3$ if possible Refer to hematologist to provide diagnostic and therapeutic management

\* Once a subject commences weekly monitoring this frequency of monitoring should continue until the platelet count returns to the normal range ( $\geq 140,000/\text{mm}^3$ ) for 2 successive values.

\*\* Recovery in platelet count may be accelerated by administration of high dose steroids. Treatment guidelines for immune thrombocytopenia (Provan et al. 2010) recommend Dexamethasone 40 mg daily for 4 days every 24 weeks for 1-4 cycles; Prednis(ol)-one 0.5-2 mg/kg/d for 2-4 weeks then taper; or Methylprednisolone 30 mg/kg/day for 7 days (note: may require continuation with oral steroids after methylprednisolone).

#### **8.6.4 Stopping Rule for Documented Severe Hypoglycemia**

In the event of a first instance of documented severe hypoglycemia, dosing of a subject with Study Drug will be suspended temporarily. The need to adjust the background medication and the suitability of the subject for continued dosing will be determined by the Investigator in consultation with the Study Medical Monitor. In the event of a second instance of documented severe hypoglycemia, after a re-challenge, dosing of a subject with Study Drug will be stopped permanently.

Dose adjustments, including dose interruptions, and/or decreasing the dose or dose frequency will be allowed for safety and tolerability. **Any proposed adjustments to treatment schedule must be discussed with, and approved by, the Study Medical monitor prior to initiation.**

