#### **8.5.6 Safety Monitoring for Hypoglycemia**

Subjects will be instructed to monitor and manage hypoglycemic episodes. Subjects will be provided with a glucometer and asked to record Self Monitored Blood Glucose (SMBG) levels weekly and report back alert values to the site. Subjects will be instructed to promptly report symptoms of hypoglycemia: headache, heart pounding, confusion, disorientation, numbness or tingling, pale skin, shakiness or tremulousness, increased appetite, anxiousness or nervousness, lightheadedness or dizziness, sweating and, weakness. If subjects suspect they might be having a hypoglycemia reaction, they should check their blood glucose using their meters as soon as possible, before treatment if possible, provided they feel it is safe to do so. If there is doubt about safety they should treat the event first, using some sugar, milk, or juice for example, then obtain and record a blood glucose value as soon as possible thereafter. The time and nature of treatment should be noted, and especially if any blood glucose result was before or after treatment. If a subject presents with symptoms of hypoglycemia, the Investigator will need to take immediate action to confirm the subject's glucose level and treat the subject accordingly. Severe hypoglycemia will be qualified as a SAE only if it fulfills SAE criteria.

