#### ***Severe Hypoglycemia***

Requires assistance of another person to actively administer carbohydrates, glucagon, or take other corrective actions. Glucose concentrations may not be available during an event. Neurological recovery following glucose levels returning to normal considered sufficient evidence that event was induced by low glucose concentration.

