### *Probable Symptomatic Hypoglycemia*

Typical hypoglycemia symptoms not accompanied by blood glucose determination but likely caused by blood glucose  $\leq 70$  mg/dL ( $\leq 3.9$  mmol/L).

A **documented severe hypoglycemic event** is defined as one in which the subject requires the assistance of another person to obtain treatment for the event and has a blood glucose level  $\leq 70$  mg/dL ( $\leq 3.9$  mmol/L). The rescue treatment of hypoglycemia may include IV glucose or buccal or intramuscular glucagon.

The definition of severe symptomatic hypoglycemia includes all episodes in which neurological impairment was severe enough to prevent self-treatment and which were thus thought to place subjects at risk for injury to themselves or others.

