#### **8.10.1.1 Allowed Concomitant Therapy**

Ibuprofen may be used for symptomatic pain relief. Any other therapy for pain (including OTC medications such as acetaminophen) should be approved by the Sponsor Medical Monitor or designee.

Any medications deemed necessary by the Investigator are allowed in response to an AE that requires drug therapy, except those listed in the disallowed concomitant therapy. In such cases, the Investigator must consult the Sponsor Medical Monitor to decide on subject continuation or withdrawal from the study.

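### Protocol 8.6.4 forces a dosing hold only when severe hypoglycemia comes with a glucose of 70 mg/dL or less, so an assisted event without such a reading triggers no hold and does not count as a first instance (minor)

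*Protocol*

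**What the plan says.** Protocol 8.6.4 has two steps. The first is a hold: "In the event of a first instance of documented severe hypoglycemia, dosing of a subject with Study Drug will be suspended temporarily". During it, "The need to adjust the background medication and the suitability of the subject for continued dosing will be determined by the Investigator"; the Study Medical Monitor is to be consulted. The second is a permanent stop, which applies "In the event of a second instance of documented severe hypoglycemia, after a re-challenge". Both steps use the documented severe category.

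Section 8.5.6 defines that category near the end of its classification, as an event in which the subject "requires the assistance of another person to obtain treatment for the event and has a blood glucose level" of 70 mg/dL or less. No timing is set for the reading.

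Under its Severe Hypoglycemia subheading, the same section classes an event as severe because another person had to help. It adds "Glucose concentrations may not be available during an event" and "Neurological recovery following glucose levels returning to normal considered sufficient evidence that event was induced by low glucose concentration". No low value is required there.

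Section 8.5.6 also says that when a subject presents with symptoms, "the Investigator will need to take immediate action to confirm" the glucose level and treat accordingly. Where an adverse event needs drug therapy, 8.10.1.1 adds: "In such cases, the Investigator must consult the Sponsor Medical Monitor to decide on subject continuation or withdrawal from the study".

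**The concern.** The protocol accepts an assisted event without a low reading as severe, and then leaves it outside the only hypoglycemia rule that requires a dosing action. The case is foreseeable. Section 8.5.6 tells subjects who doubt their safety to treat first and measure afterwards, so the only reading may be missing or already above 70 mg/dL.

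What is at stake is the order of events. The 8.6.4 suspension puts review of background medication and of suitability for further dosing ahead of the next injection. Sulfonylureas are permitted (Protocol 5.1), so that review has a purpose. Without the suspension, the next dose stays due within 7 days in Cohort A or 28 days in Cohorts B and C unless someone chooses to interrupt. If a documented event follows later, it is handled as the first.

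The stake is not a rapid fall in exposure: Protocol 2.3.4 gives a terminal half-life of 3 to 5 weeks.

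**Working it through.** The plan gives no figure on this point to reproduce. The check compares definitions and then prices the fix.

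**1. Which events reach the 8.6.4 trigger**

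| Event | Severe under 8.5.6 | Documented severe under 8.5.6 | Hold required by 8.6.4 |
|---|---|---|---|
| Assisted, glucose ≤ 70 mg/dL before or after treatment | Yes | Yes | Yes |
| Assisted, no reading, neurological recovery | Yes | No | No |
| Assisted, treated first, only reading > 70 mg/dL | Yes | No | No |

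**2. Whether another provision forces a hold in the last two rows**

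- Protocol 8.5, the second paragraph of 8.6.4, and 8.7 permit interruption; none requires it.
- Protocol 8.10.1.1 requires consultation when an adverse event needs drug therapy. It requires no hold, and an event treated with carbohydrate alone may fall outside it.
- Protocol 8.8 points to the stopping rules in 8.6.1 to 8.6.3 and to adverse events that necessitate discontinuation. It adds no hypoglycemia rule.
- SAP 2.4.1 has the Sponsor's medical monitor review all adverse events on an ongoing basis, with no link to the next dose.

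So no hold is forced. That the event is not counted as a first instance follows from the wording of 8.6.4; no sentence says so expressly.

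**3. What the fix changes**

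Let D be an assisted event with glucose ≤ 70 mg/dL and U one without.

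| Order of two events | Current rule | Revised rule |
|---|---|---|
| D, D | Suspend, then permanent stop | Suspend, then permanent stop |
| D, U | Suspend, then nothing mandatory | Suspend, then suspend and review |
| U, D | Nothing mandatory, then suspend | Suspend, then permanent stop |
| U, U | Nothing mandatory | Suspend, then suspend and review |

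The table assumes re-challenge between the events. Only U then D newly reaches the permanent stop. The rows describe how the rule behaves and carry no probabilities.

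**4. What a suspension costs**

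Inputs: 26 planned doses in A and 6 in B and C (Protocol 8.1). The Per Protocol minimum is 25 in A and 5 in B and C (Protocol 10.3), or 22 in A and 5 in B and C (SAP 3.2.4). Share of planned dose lost = doses lost / doses planned.

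- One dose lost: A 1/26 = 3.8%; B and C 1/6 = 16.7%. Doses left are 25 and 5, which meet both documents' minimums.
- Two doses lost (a second suspension): A 2/26 = 7.7%; B and C 2/6 = 33.3%. Doses left are 24 and 4. In B and C, 4 is below the minimum of 5 in both documents. In A, 24 is below the protocol's 25 but above the SAP's 22.

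These figures assume that each review ends within one dosing interval. A short hold may cost nothing, because 8.1 lets an injection be rescheduled if two doses are at least 2 days apart.

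**The case against.** The glucose requirement looks deliberate. The word documented stands in the title of 8.6.4 and in both trigger sentences, and Protocol 8.5 likewise makes permanent discontinuation depend on confirmed criteria. That is a good reason to demand a value before a permanent stop, and the fix keeps it there. It is a weaker reason to skip a reversible hold after an event that the protocol already accepts as severe.

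The remaining case is also small, and this stands. Subjects have glucometers and are told to test before treatment if safe, otherwise as soon as possible afterwards. A post-treatment value of 70 mg/dL or less qualifies. Insulin is excluded (Protocol 5.2). IV glucose or glucagon, named in 8.5.6 as possible rescue, would bring in the consultation in 8.10.1.1. The Sponsor's medical monitor sees all adverse events, and the DSMB reviews safety.

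Three stronger readings are tempting, and the documents do not support them:

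- A reader might infer that such an event meets no safety response. The provisions just listed show otherwise; what is missing is a required hold and a guarantee of review before the next dose.
- A reader might infer that the protocol contradicts itself, since dosing waits after an unconfirmed stopping-level laboratory result (8.5) or an unreportable platelet count (6.2, 8.6.3). Those samples can be redrawn. A glucose value missed during a past event cannot be recovered, so the comparison is loose.
- A reader might turn the four event orders into a share of patients at risk. They are unweighted, and the documents give no event rate.

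**Conclusion.** The gap is real on the text: an assisted event without a glucose of 70 mg/dL or less forces no dosing hold and, by the wording of 8.6.4, is not a first instance. It is minor. The conclusion rests on reading the 8.6.4 term as the one defined in 8.5.6, which is the only definition of documented severe in the documents. The frequency cannot be computed; that events will be few is a judgement from the exclusion of insulin, tempered by the permitted sulfonylureas.

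The effect on reporting is limited. SAP 3.5.2 refers to Protocol 8.6 for its rule table, so its stopping-rule count follows the documented definition. It does not say whether the monitoring-rule part covers assisted events without a reading. A reader might infer that these events vanish from the report; they do not, because reported events still appear in the TEAE tables under SAP 3.5.1.

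**What to change.** In Protocol 8.6.4, apply the first-instance temporary suspension, pending review by the Investigator and Study Medical Monitor, to any event meeting the Severe Hypoglycemia definition in 8.5.6, with or without a glucose value. Count that event as the first instance. Keep the glucose criterion for the permanent stop; a second event without a qualifying reading is again suspended and reviewed.

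This takes about two sentences. The site must already establish whether assistance was needed in order to apply the current rule. The downside is an occasional hold for an event that was not biochemically confirmed, at the dose cost worked out above. A second suspension could remove a subject from the Per Protocol Set, mainly in Cohorts B and C. Repeated events that never yield a qualifying reading would still not reach the permanent stop automatically.

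Optional: in the SAP 3.5.2 table, show all assisted events and the glucose-documented subset on separate rows. This depends on whether the eCRF captures the need for assistance, which the documents do not show. A reference to 8.6.4 in the Protocol 8.8 list would be a tidy-up only.
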